5.1. Overall Design

This is a Phase 1, single-center study in healthy subjects to be conducted in 4 parts:

- Part A will be a subject- and investigator-blind, placebo-controlled, randomized, single-ascending dose (SAD), 3-period crossover study to evaluate safety, tolerability, and PK of LY3154885 in 2 alternating cohorts.
- Part B will be a subject- and investigator-blind to LY3154885/placebo, single-period, drug-drug interaction study with itraconazole.
- Part C will be a subject- and investigator-blind, placebo-controlled, randomized, 14-day multiple-ascending dose (MAD), parallel-group, 3-cohort, single-period study to evaluate safety, tolerability, and PK of LY3154885.
- Optional Part D will be an open-label, 3-period 3-sequence PK study of LY3154885 administered using a capsule or tablet formulation. Part D will also include a pilot food effect evaluation.

Study governance considerations are described in detail in [Appendix 3](#).

5.1.1. Part A (Single-Ascending Dose)

Part A will be conducted in 2 alternating cohorts (Cohorts 1 and 2), each consisting of approximately 12 subjects who will participate in up to 3 study periods. The planned doses of LY3154885 to be tested are 15, 45, 100, 200, 400, and 500 mg (see Section [5.5](#) for details).

Sentinel dosing will be used in Part A of the study. For all dose levels, LY3154885 and placebo will be administered first to 2 subjects (1:1 LY3154885:Placebo) in a blinded manner. These subjects will be followed up for 24 hours postdose; if the dose is well tolerated, dosing of the remaining 10 subjects in the cohort at the same dose level may begin.

Each subject in Cohorts 1 and 2 will be randomized to receive 2 single oral doses of LY3154885 and 1 oral dose of placebo as a capsule formulation over 3 study periods in a crossover fashion. For each study period, it is intended that 8 subjects will receive LY3154885 and 4 subjects will receive placebo.

In Period 1, subjects will be admitted to the clinical research unit (CRU) on the afternoon of Day -2 for set up of baseline ambulatory blood pressure monitoring (ABPM) (see Section [9.4.4](#)) and on Day -1 for Periods 2 and 3. Subjects will undergo an overnight fast (Section [6.3.1](#)) before dosing with LY3154885 or placebo as a single oral dose on Day 1 and will remain inpatient for at least 48 hours after dosing (until Day 3), after which they may be discharged at the discretion of the investigator. The washout time between doses for a given subject will be at least 7 days. A poststudy follow-up visit will be conducted at least 7 days after the final dose.

All available safety data, including AEs, vital signs (blood pressure [BP] and pulse rate [PR]), ECGs, and clinical laboratory tests, from all subjects dosed will be assessed prior to escalating to

the next dose level (see Section 10.3.5). Safety data must include data from at least 2 days from a minimum of 6 subjects who received LY3154885. The investigator and sponsor will review the data, with the investigator remaining blinded. If dose escalation is terminated prior to reaching Dose 6 because of tolerability issues, previous dose levels may be repeated or lower/intermediate dose levels may be tested.

Subjects will provide total urine collections for the 36 hours postdose in each period for exploratory metabolism and potential assessment of drug absorption and renal elimination; an additional blood sample will be collected to determine serum creatinine measurements.

Figure HUAA.5.1 illustrates the study design for Part A.

	Period 1		Period 2		Period 3	
Cohort 1 (n=12; 8LY:4PL)	Dose 1 LY or PL	≥7 day washout	Dose 3 LY or PL	≥7 day washout	Dose 5 LY or PL	≥7 day washout
Cohort 2 (n=12; 8LY:4PL)		Dose 2 LY or PL	≥7 day washout	Dose 4 LY or PL	≥7 day washout	Dose 6 LY or PL

Safety review completed after each dose level prior to escalation

Abbreviations: LY = LY3154885; n = number of subjects; PL = placebo.
Each subject will receive 2 doses of LY3154885 and 1 placebo dose.

Figure HUAA.5.1. Illustration of study design for Part A.

5.1.2. Part B (CYP3A4 Inhibition)

Part B will consist of approximately 12 subjects [9 LY3154885; 3 placebo] and will assess the effect of itraconazole, a CYP3A4 inhibitor, on the safety, tolerability, and PK of LY3154885. The LY3154885 dose to be studied in Part B will be determined based on safety, tolerability, and PK data from Part A and will be administered as a capsule formulation. See Section 5.5 for further LY3154885 dose justification.

As detailed in the Schedule of Activities (Section 2), subjects will be admitted to the CRU in the afternoon of Day -2 for set up of baseline ABPM (see Section 9.4.4) and will undergo an overnight fast (see Section 6.3.1) before receiving a single oral dose of LY3154885 or placebo on Day 1. Subjects may be discharged from the CRU on Day 3 and will be re-admitted on Day 7. There will be a 7-day washout period followed by 10 days of dosing with 200 mg itraconazole (twice daily on Day 8 [dose separated by 12 hours], then once daily on Days 9 through 17). See Section 6.3.1 for the fasting requirements for the itraconazole dosing. Subjects will be discharged from the CRU on Day 9 after receiving their dose of itraconazole and will be self-dosing on an outpatient basis from Days 10 through 12. Subjects will be asked to complete a diary card to document the actual date and time of dose administration.

Subjects will be re-admitted to the CRU in the evening of Day 12 and will undergo an overnight fast (see Section 6.3.1) before receiving a single oral dose of LY3154885 or placebo on Day 14, approximately 1 hour after the dose of itraconazole. Blood sampling for PK purposes (LY3154885 and itraconazole) will occur according to the Schedule of Activities in Section 2. Subjects will remain in the CRU until discharge on the morning of Day 18, approximately 24 hours after the final dose of itraconazole.

Figure HUAA.5.2 illustrates the study design for Part B.

[figure not shown]

Figure HUAA.5.2. Illustration of study design for Part B.

5.1.3. Part C (Multiple-Ascending Dose)

The decision to conduct Part C will be made after review of safety, tolerability, and PK data from Parts A (SAD) and B (CYP3A4 Inhibition).

[figure not shown]
Part C will explore up to 3 dose levels in 3 separate cohorts (Cohorts 4 to 6) of healthy subjects. Each cohort will consist of approximately 12 subjects (9 LY3154885; 3 placebo) dosed daily for 14 days with a capsule formulation.

Subjects will participate in a single study period consisting of 14 days of once-daily dosing with LY3154885 or placebo; study drug will be administered as a single oral dose in the morning under fasted conditions (see Section 6.3.1). Subjects will be admitted to the CRU on the afternoon of Day -2 for set up of baseline ABPM (see Section 9.4.4) and will be required to remain in-house for at least 48 hours after dosing (Day 3), and at the discretion of the investigator. As detailed in the Schedule of Activities (Section 2), subjects will attend the CRU on Days 4, 5, 6, 9, and 10 on an outpatient basis for daily dosing and will be permitted to leave the CRU at the discretion of the investigator. Pharmacokinetic sampling will be conducted as detailed in Section 2. To assess CV effects and potential accommodation over time, ABPM will

be included on Day -1 (baseline) and on Days 1, 2, 7, 11 and 12, and 14. A poststudy follow-up visit will be conducted approximately 7 days after discharge.

The doses evaluated will be selected based on emerging data from Parts A and B and from the lower doses from Part C (see Section 5.5 for details). If the safety data do not support increasing the dose in subsequent cohorts, then a dose may be repeated or lower/intermediate doses may be explored. The PK data obtained during the study may be used to assist in dose-escalation decisions, but such data are not required for dose-escalation purposes. For the safety review prior to dose decisions between cohorts, all available safety data (AEs, vital signs, ECGs, and laboratory results) to Day 14 from at least 6 subjects taking LY3154885 must be reviewed by the sponsor and investigator. In addition, each cohort (including at least 6 subjects treated with LY3154885) will complete dosing to Day 14 prior to the next cohort being admitted to the CRU for dosing.

Figure HUAA.5.3 illustrates the study design for Part C.

Abbreviations: LY = LY3154885; PL = placebo; QD = once daily.

Figure HUAA.5.3. Illustration of study design for Part C.

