Informed consent	X													
Admission to CRU		X				D6		D10					Afternoon admission.	
Discharge from CRU						D3		D8		X				
Medical history	X													
AE/medication review			X	X	X	X	X	X	X	X	X			
Height/weight	X		X							X			Height at screening only.	
Neurological exam (hours)	X			Predose, 4, (8)	24	48	Predose, 4, (8)	24, 48		X	X		The 8-hour time point is optional.	
LY3154885/Placebo administration				X	X	X	X	X					On Days 4, 5, 6, 9, and 10, subjects will receive their dose of LY3154885/placebo at the CRU and then may be discharged at the discretion of the investigator.	
Vital signs (BP, PR [supine], temperature) (hours)	X		X	Predose, 2, 4, 8, 12	Predose, 2, 4, 8, 12	Predose, 2	Predose, 2, 4, 8, 12	Predose, 2	Predose, 2, 4, 8, 12	X	X	X	Time points on outpatient dosing days (Days 4, 5, 6, 9, and 10) may be adjusted based on emerging data from Part A and/or if clinically indicated. On Days 1 to 14, temperature will be measured at predose only.	

continued

Study Schedule Protocol J1Z-MC-HUAA (Part C: Multiple-Ascending Dose – Single Period) (continued)

Procedure	Screening	Days										ED	Follow-up	Comments
		-28 to -3	-2	-1	1	2	3-6	7	8-13	14	15			
ABPM			X	X	X		X	D11&12	X					The ABPM on Day -1 is a 24-hour collection for baseline measurement. On dosing days, the ABPM recording will be initiated approximately 2 hours prior to dosing for measurement of predose baseline.
Clinical laboratory tests	X	X		Predose			Predose			X	X	X		See Appendix 2 , Clinical Laboratory Tests, for details. PI must review Day -2 result prior to dose on Day 1.
Pregnancy test	X	X					Predose			X	X	X		Serum test at screening and admission; urine test at all other time points per investigator discretion. Women with confirmed nonchildbearing potential status can be exempted from further pregnancy tests during the study after screening.
PE/MA	X			Predose						X	X	X		Full PE/MA at screening and prior to final discharge from the study. Symptom-directed PE/MA at all other time points and as deemed necessary by the investigator.

continued

Study Schedule Protocol J1Z-MC-HUAA (Part C: Multiple-Ascending Dose – Single Period) (concluded)

	Screening	Days										ED	Follow-up	Comments
Procedure	-28 to -3	-2	-1	1	2	3-6	7	8-13	14	15		Approx 7 days after discharge		

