3.2. Background

LY3154885 is a D1 PAM. By increasing the affinity of the D1 receptor for dopamine, a D1 PAM should amplify the response to endogenous dopamine, increasing D1 tone when and where dopamine is released. By increasing the affinity of the D1 receptor for dopamine, D1 PAMs amplify the response to endogenous dopamine, increasing D1 tone when and where dopamine is released (Svensson et al. 2017; Bruns et al. 2018).

This mode of activity is in contrast to direct acting D1 agonists, which activate all D1 receptors to which they have access for as long as they are present. Some D1 agonists also show rapid development of tolerance due to constant activation of the D1 receptor. In contrast, because the mechanism of action of a D1 PAM is dependent on endogenous dopamine tone and thus subject to normal feedback control, a D1 PAM should have a much lower propensity for overstimulation and desensitization.

LY3154885 has demonstrated a favorable safety profile in good laboratory practice (GLP)-compliant toxicology and safety pharmacology studies to support clinical trials, with cardiovascular (CV) and central nervous system (CNS) effects that are transient, monitorable,

and void of correlating adverse pathologic changes. CCI

CCI

LY3154885 has demonstrated suitable absorption, distribution, metabolism, and excretion properties in in vitro experiments and in nonclinical in vivo studies to warrant clinical investigation. The compound is lipophilic and neutral, with acceptable solubility and high permeability. It is eliminated mainly via hepatic metabolism by CYP3A4 and UDP-glucuronosyltransferase (UGT). In humans, LY3154885 is projected to have low oral clearance and a half-life of approximately 12 hours. The drug-drug interaction risk with LY3154885 is considered low based on in vitro data and projected human dose and exposures. However, since there is some uncertainty about the extent that CYP3A4 metabolism contributes to the overall clearance of LY3154885, this will be evaluated as part of this study by coadministering LY3154885 with itraconazole, a strong CYP3A4 inhibitor. Itraconazole is predicted to result in a LY3154885 area under the concentration versus time curve (AUC) that is 2.6-times the AUC when LY3154885 is administered alone.

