7.4.1. Dose Decision/Escalation

By nature of being a dose-escalation study, data will be evaluated on an ongoing basis until the maximum tolerated dose (MTD) is determined or the highest planned dose is administered. The highest dose level that is tolerated will be designated as the MTD.

Safety data will be the primary criteria for the dose escalation. In addition, if available at the time of the dose-escalation decision, PK results will be used as supporting data. No dose escalation can occur without prior discussion and agreement between the investigator and the Lilly study team. See Sections 5.1.1 and 5.1.3 for further details.

Safety data, in particular AEs, SAEs, BP, PR, and adverse laboratory abnormalities, will be independently assessed by the investigator and will be considered related to the investigational medicinal product, unless there is clear evidence that the event is not related.

If any of the following scenarios occur, dosing at the current level and further dose escalation will be discontinued:

- 1) a single subject experiences an SAE that is related to LY3154885 administration
- 2) 2 subjects experience a clinically significant event of persistent tremors that is deemed to be related to LY3154885 administration
- 3) 2 subjects experience clinically significant increases in scheduled vital signs that are deemed to be related to LY3154885 administration
- 4) 2 or more subjects at 1 dose level experience other moderate or severe treatment-related AEs that impair normal activities and are deemed to be related to LY3154885 administration

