10.3.5. Data Review During the Study

Access to safety and tolerability data is scheduled to occur after every dosing session (see Sections 5.1.1, 5.1.2, 5.1.3, and 5.1.4 [study design], and 5.5 [dose justification] for further details). Pharmacokinetic data will be reviewed to guide implementation of this study (such as adjustment to blood sampling time) and to support dose escalations at the following decision points:

- In Part A, LY3154885 PK data (up to 48 hours postdose) from Doses 1 to 3 will be reviewed prior to administration of Dose 5
- In Part A, LY3154885 PK data (up to 48 hours postdose) from Dose 5 will be reviewed prior to administration of Dose 6
- In Part B, LY3154885 PK data (up to 96 hours postdose) will be reviewed to inform a decision on the conduct of Part C and D
- In Part C, LY3154885 PK data (up to 24 hours postdose on Day 15) from the low dose (Cohort 4) will be reviewed prior to administration of the high dose (Cohort 6)

The investigator and the Lilly sponsor team will make the determination regarding dose escalation based upon their review of the safety and tolerability data and any available PK data. Data reviews may be added as deemed appropriate by the sponsor without a protocol amendment.

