Appendix 6. Protocol Amendment J1Z-MC-HUAA(b) Summary

Single- and Multiple-Ascending Dose, Safety, Tolerability, and Pharmacokinetic Study with LY3154885 in Healthy Subjects

[figure not shown]
Overview

Protocol J1Z-MC-HUAA “Single- and Multiple-Ascending Dose, Safety, Tolerability, and Pharmacokinetic Study with LY3154885 in Healthy Subjects” has been amended. The new protocol is indicated by Amendment (b) and will be used to conduct the study in place of any preceding version of the protocol.

After receipt of feedback from the US Food and Drug Administration, the following changes have been made to this protocol:

- Section 5.1.3. Part C (Multiple-Ascending Dose) has been modified to extend the review period for safety data from 6 to 14 days prior to making a final decision about the dose level to be administered to the next cohort.

CCI

- Text within section 5.5 (Justification for Dose) has been modified to reflect the inclusion of the monkey NOEL data.

Other changes made to the protocol are as follows:

- Section 1 (Protocol Synopsis):
 - The language has been updated to state that for parts A, B, C, and D, subjects will be admitted to the CRU (Day -2, first period) in the afternoon.
 - Evening admission has been deleted.
- Section 2 (Schedule of Activities – Parts A – D):
 - The comment section in the physical examination/medical assessment (PE/MA) row has been updated to state that a full PE/MA will be conducted prior to final discharge from the study.

- Section 2 (Schedule of Activities – Part A):
 - “Single safety” has been added to the description within the 12-lead ECG row.
 - Also on this row, ECG measurements at hours 2 and 4 (Day 1) have been added, and
 - measurements at hours 0.5, 1, 2, 3, 4, 5, 6, 8, and 12 (Day 1) and 36 (Day 2) have been deleted.
 - The comments previously contained within the comment section in this row have been deleted.
- Section 2 (Schedule of Activities – Parts B and C):
 - A requirement to conduct clinical laboratory tests on Day -2 has been added. A comment has been added to state that the PI must review the Day -2 laboratory results before dosing on Day 1.
- Section 2 (Schedule of Activities – Parts B and C):
 - The comment associated with the ABPM row has been updated to include the term “predose”.
- Section 2 (Schedule of Activities – Part C):
 - The comments have been updated within the admission to CRU row to reflect that admission will occur in the afternoon rather than the evening.

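### The Part C between-cohort safety review can be met with laboratory data from only the first 6 of 14 doses; the Day 15 panel already scheduled is not required before the next dose level is given

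*Protocol*

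**What the plan says.** Part C gives 14 once-daily doses in up to three ascending cohorts (Cohorts 4 to 6). Protocol Section 5.1.3 sets two conditions between cohorts. First, the sponsor and investigator have a minimum set of data to go through ahead of a dose decision: "all available safety data (AEs, vital signs, ECGs, and laboratory results) to Day 14 from at least 6 subjects taking LY3154885 must be reviewed". Second, each cohort "will complete dosing to Day 14 prior to the next cohort being admitted to the CRU for dosing".

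The Part C Schedule of Activities places clinical laboratory tests at screening, Day -2, Day 1 predose, Day 7 predose, Day 15, early discontinuation and follow-up. The Day 8-13 and Day 14 cells are empty. The comment on that row adds: "PI must review Day -2 result prior to dose on Day 1".

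Section 7.4.1 makes safety data the primary criterion for escalation and names laboratory abnormalities among them: "Safety data, in particular AEs, SAEs, BP, PR, and adverse laboratory abnormalities, will be independently assessed by the investigator". Section 10.3.5 lists decision points for PK review. The only Part C entry concerns the step up to Cohort 6, the high dose: "LY3154885 PK data (up to 24 hours postdose on Day 15) from the low dose (Cohort 4) will be reviewed prior to administration".

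Appendix 6 says that amendment (b), after regulatory feedback, changed Section 5.1.3 to "extend the review period for safety data from 6 to 14 days prior to making a final decision" on the next dose level.

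**The concern.** The rule reads as though laboratory safety is checked over the full dosing period before the dose goes up. Set against the schedule, it does not ensure that. The last scheduled panel inside the Day 14 cut-off is on Day 7, and the panel that would cover all 14 doses falls one day outside it. For scheduled laboratory data, the extension from 6 to 14 days therefore adds only the Day 7 predose draw.

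At stake is the protection of the next cohort. A laboratory change that needs more than about a week of dosing and causes no symptoms, such as a rise in liver enzymes, need not have been looked for before a higher dose is started in new subjects. AE review and vital signs cannot be relied on to show a change of that kind. This is a gap in a stated safety requirement, not a contradiction in the text.

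**Working it through.** **1. Reading the schedule.** The column order is screening, Day -2, -1, 1, 2, 3-6, 7, 8-13, 14, 15, early discontinuation, follow-up. As a check on alignment, the ABPM row read the same way gives Days -1, 1, 2, 7, 11 and 12, and 14, which is the list in Section 5.1.3. Appendix 5 gives a second check. It counts 4 Part C laboratory samples apart from screening, which matches Day 1, Day 7, Day 15 and follow-up, without the Day -2 draw that amendment (b) added.

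**2. Panels and doses inside the required window.** The Day 7 sample is predose, so 6 doses precede it.

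| Laboratory cut-off | Scheduled on-drug panels | Doses before the last panel |
|---|---|---|
| Day 6 (former rule) | 0 | none |
| Day 14 (current rule) | 1 (Day 7 predose) | 6/14 = 43% |
| Through Day 15 | 2 (Day 7, Day 15) | 14/14 = 100% |

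Under the current rule, 14 − 6 = 8 doses (8/14 = 57%) are followed by no scheduled panel in the required data.

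**3. Whether another rule closes the gap.** Admission of the next cohort depends on dosing to Day 14, not on Day 15 results. The Section 10.3.5 entry reaches Day 15, but only for PK and only for Cohort 4 before Cohort 6. It leaves out laboratory results, the Cohort 4 to 5 step, and Cohort 5 data before Cohort 6.

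**4. Calendar.** Dosing is in the morning and admission in the afternoon, so the next cohort can be admitted on the preceding cohort's Day 14. That is the new cohort's Day -2. The preceding cohort's Day 15 is then the new cohort's Day -1, and Day 16 is its Day 1. The earliest next first dose therefore falls about 24 hours after the Day 15 draw.

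**5. Exposure or duration.** Section 3.2 states: "In humans, LY3154885 is projected to have low oral clearance and a half-life of approximately 12 hours". The fraction of steady state after 6 daily doses is 1 − 2^(−6×24/t½):

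- t½ = 12 h: 1 − 2^(−12) = 99.98%
- t½ = 24 h (assumed): 1 − 2^(−6) = 98.4%
- t½ = 48 h (assumed): 1 − 2^(−3) = 87.5%

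At the projected half-life, the Day 7 panel already reflects full exposure. What it lacks is duration.

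**6. What the Day 15 panel could show.** Suppose a laboratory abnormality first appears in week 2 in a proportion p of LY3154885 subjects and is present on Day 15. The documents give no value for p, so a range is assumed. With the minimum of 6 subjects, P(at least one case) = 1 − (1 − p)^6:

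- p = 0.10: 1 − 0.90^6 = 0.469
- p = 0.20: 1 − 0.80^6 = 0.738
- p = 0.30: 1 − 0.70^6 = 0.882

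Within the scheduled draws of the current minimum, the corresponding probability is zero.

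**The case against.** The strongest reply is that a panel already drawn is unlikely to be ignored. Section 10.3.5 provides for access to safety data after every dosing session and lets the sponsor add reviews. Section 9.2 has the investigator document review of each laboratory report. Section 9.4.8 has the sponsor and investigator monitor safety throughout, with laboratory analytes on the sponsor's periodic list. Section 7.4.1 bars escalation without their agreement. The calendar helps too: the Day 15 sample exists before the next cohort can be dosed, so harm requires back-to-back cohorts and a decision taken without waiting for it. Unscheduled or early-discontinuation panels in week 2 would also count as available data.

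Further, the 10-30% rates have no basis in the documents, and the detection probabilities are a benefit only if the Day 15 results would otherwise go unseen. The unredacted nonclinical text describes cardiovascular and CNS effects that are transient and monitorable, not a delayed laboratory signal. Part C is capped at doses and exposures tolerated in Parts A and B. Vital signs and AE review run through Day 14, and Day 14 has ECGs to 12 hours.

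All of this stands as a limit on size. It makes an actual miss improbable and confines the gap mainly to laboratory data. It does not close the gap, because none of these provisions makes Day 15 results a condition of escalation. The lack of a documented hazard is also weak reassurance in a first-in-human study where part of the toxicology text cannot be read.

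**Conclusion.** The concern holds. As written, the minimum Part C review can be satisfied with one scheduled on-drug laboratory panel per subject, after 43% of the doses, while the panel covering all 14 doses sits one day beyond the cut-off and is not required. The counts come directly from the schedule. The steady-state figure rests on the projected 12-hour half-life, and the 47%, 74% and 88% detection figures rest on assumed rates and on the abnormality persisting to Day 15. The size of the problem also depends on how often reviewers would decide without available Day 15 results, which cannot be estimated from the documents and is probably low. It should be fixed because it concerns a stated safety requirement and the remedy costs almost nothing.

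**What to change.** Reword Section 5.1.3 so that, for the minimum 6 LY3154885 subjects, the required review runs through the Day 15 discharge assessments already scheduled: the laboratory panel and the 24-hour ECG. Preferably add the Day 15 neurological examination. Section 5.1.3 does not list that examination now, but in Part C it is not scheduled between 48 hours after the Day 7 dose and Day 15, and persistent tremor is a stopping criterion in Section 7.4.1. State that the next cohort's first dose may not be given until this review is complete. Admission on Day -2 can go ahead while results are pending.

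The cost is one sentence and no new test. The protocol already relies on Day -2 laboratory results being reviewed before the Day 1 dose, so turnaround is under two days. Against an earliest first dose on Day 16, the added wait is about one day at most for each of the two planned escalations.
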